	
To provide a preliminary assessment of the prognostic value of CTC data (positivity and gene expression) in predicting post-RP PCa metastasis development, overall survival and cancer specific survival.
 
To provide evidence and data which can be used to design a future clinical trial of a CTC- based intervention to be used to guide therapeutic choice in the management of high-risk localised PCa.
 
To evaluate the longer-term prognostic value of CTC detection and CTC gene expression for metastases and cancer-specific survival.
 
Primary endpoint
 
The primary outcome is post-RP treatment failure during the first 4.5 years of follow up from start of recruitment.
 
Post-RP treatment failure is defined as a PSA $\geq 0.2\text{mg/ml}$ at the routine PSA test 3 months after RP (commonly called 'failure to nadir') and remaining at this level or further increase afterwards without further treatment, or imaging detected appearance of cancer lesions.
 
Cancer lesions detected by imaging without a PSA rise might include neuroendocrine PCa and lesions detected by PSAM-PET. This combined post-RP treatment failure primary endpoint will maximally capture all the clinically significant cancer appearance events.
 
Secondary endpoints
 
BCR during the first 4.5 years of follow up: PSA $\geq 0.2\text{ng/ml}$ at any time post-RP and remaining at this level or further increase afterwards without further treatment.
 
Metastasis (any location)-free survival during the first 4.5 years of follow up. Only 5% of subjects with distant metastasis event (based on traditional imaging technologies) within this time frame (4-6).
 
Metastasis (any location)-free survival at 10 years follow up. to confirm that metastatic event rates have increased among the positives, i.e. a declining rate of "false positives".
 
Deaths from any cause during the first 4.5 years of follow up
 
Overall survival at 10 years of follow up.
 
Prostate cancer specific deaths during the first 4.5 years of follow up. Expected to be 2% or less based on previous studies in the post RP context.
 
Prostate cancer specific survival at 10 years of follow up. Our hypothesis is that most if not all of the patients dying of PCa will be in the CTC positive group.

Target sample size	294

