With an anticipated drop out of 40% due to either use of neo-adjuvant ADT or failure to consent in patients sent the PIS, we further anticipate 294 patients will contribute blood samples prior to RP. There is a target of 200 blood samples from eligible participants, who subsequent to having had RP do not have a positive surgery margin or other evidence of locally remaining disease, and do not subsequently have ADT (adjuvant ADT) or radiotherapy. It is intended that recruitment will continue until this target has been met.

6. Patient recruitment, sample collection, lab CTC analysis and follow-up procedures

Patients will be recruited (months 1-24) at UCLH, where the UK largest urological surgery centre is located and performs robot-assisted RP on PCa patients referred from several regional hospitals. The clinical team at UCLH will identify eligible patients who will be approached by the clinical research fellow (CRF) employed on the research project or the clinical care team for informed consent using the consent forms specifically designed for this project for blood collection and future research. Non-metastatic disease will be based on the current standard diagnostic imaging methods including CT/MRI and PSMA-PET/bone scan. A pre-surgery PSA test will be performed routinely at UCLH.

2 x 10 ml blood samples will be collected (months 1-27) using the lavender cap EDTA tube according to our established method from each consented patient by the CRF or the clinical care team at UCLH during the pre- and post-RP PSA test blood sampling, and taken to the laboratory at Barts Cancer Institute, [name] either by the CRF, a tissue bank acquisition officer (TBAO)(in the absence of the CRF) or the postdoc (anonymise samples transfer in the absence of CRF and TBAO) under the signed material transfer agreement (MTA), at room temperature. The samples will be transported in

Protocol for spin off research project- Circulating tumour cells as biomarkers to predict prostate cancer metastasis for treatment stratification of localised cancer

designated sample carrier using a taxi service. No public transport is to be used for moving samples between sites.

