Each patient will be allocated a unique ID and will be used by the lab research team. This unique ID will be recorded in the tissue bank database for future correlation analysis of the CTC results with clinical follow-up data. Sample processing will be performed in tissue culture hood in the designated lab. The whole blood sample will be processed within 4hrs for CTC analysis after collection. Standard Operating Procedure (SOP) (C-ProMeta-1) that is generated describing sample process and analyses need to be followed. There will be fewer patients for the post-RP than the pre-surgery blood collection based on patient exclusion criteria after RP.

Based on the sample size calculation 200 patients will be recruited for both pre- and post-surgery blood sample collections for CTC analysis, which are expected to be achieved within the first two years of the project.

Patient informed consent (including the permission to conduct remote longer-term follow-up) and blood sample collection will be performed by the CRF or the clinical care team.

All patients will have a PSA test at 3 months after their RP during a routine follow-up at UCLH. A PSA ≥ 0.2 will be recorded as a treatment failure event and PSMA-PET scans will be performed as standard clinical care at the study hospitals to detect small PCa lesions. After 3 months, patients are referred back to their original referring centres. Patients with negative PSA results at three months will be followed up by telephone or online app by the study CRF in order to ascertain whether subsequent PSA tests are positive (PSA ≥ 0.2), indicating BCR, metastasis occurs as detected by cancer imaging including PSMA-PET scan or if they have received salvage treatment with hormones/radiotherapy. In addition, details of long term follow up, such as post-operative PSA results and record of adjuvant therapies, will be sourced from patients' hospital electronic medical records, or requested from their local GP or health centre. All patients will be followed-up until the end of the project for metastasis progression as detected by imaging, PCa-specific death and death from any causes. In addition to data collected within the 5-year funded period, we plan to conduct remote longer-term follow up with fully informed consent from patients at point of enrolment, including:

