The recruitment plan will be 200 patients in the first two years of the 5-year project to allow an approximate 3.5 to 4 year median follow up. Specificity is important considering the future circumstance of potentially denying patients curative surgery, if a CTC test indicates metastasis. A study size of 200 and 120 true negatives would give a 97.5% lower confidence limit on a specificity of 99% (1% false positive rate). However, it is anticipated the specificity will be low due to positive results for those who recur beyond the 5-year study. Assuming these events are due to micro-metastases at the time of surgery, observed sensitivity and specificity will be used, plus additional analyses assuming up to 20% of the events occur after the funded 5-year project⁴⁻¹¹ to estimate the real false positive and negative rates.

3). Method of analysis

Study flow and patient characteristics will be reported. Measures of accuracy will be presented with 95% confidence intervals (CIs). The primary analysis is the estimation of the sensitivity of the pre-surgery existence of CTCs for detection of RP treatment failure, i.e. BCR or progression detected by any imaging at the 4.5-year follow-up time point. Observed specificity, positive and negative prediction values will also be reported at 4.5 years of follow up, with a note to indicate that these estimates are subject to change given the long-term nature of recurrence events. Specificity will be presented over time and additional analysis accounting for artificial inflation of false positives based on increasing prevalence of events. BCR-free survival will be estimated and Kaplan-Meier curves presented.

The number of participants with recorded metastases, lymph node metastases, deaths from any cause and PCa deaths during the first 4.5 years of follow up

Protocol for spin off research project- Circulating tumour cells as biomarkers to predict prostate cancer metastasis for treatment stratification of localised cancer

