will be reported alongside the number of these participants with a positive by CTC result, and positive combined CTC result. Metastases-free, PCa-specific and overall survival will be reported during the 5 years study time frame and it is intended to perform a later analysis at 10 years of follow up. Preliminary investigation of the prognostic value of pre-surgery CTC data in terms of predicting survival outcomes will be investigated using Cox regression, with hazard ratios reported with associated 95% CIs. CTC data will be explored alongside other pre-surgery risk factors such as plasma PSA using multivariate analysis. Recurrence events and follow up CTC results will be reported and compared over time. The above analyses will be applied to the CTC gene panel. The gene panel will also be correlated with the pre- and post- RP CTC number changes and cancer progression events.

CTC results will be presented for the whole cohort who provided analysable blood samples and stratified by those included in the above analyses, and those excluded due to reasons such as a positive surgery margin, other evidence of locally remaining disease, and who subsequently have adjuvant ADT or radiotherapy.

8. Ethics

The study is a spin out project of the parent project authorised under RLTB ethics, where the main research tissue bank approval provided by the London City & East Research Ethics Committee.

9. Data handling, storage and record keeping- to describe who and how the data will be handled, which data nodes will be used, where it will be stored and security of the data

The CRF (funded by QMUL, but with contract at UCLH) will be part of the study management group and will act as the contact point between UCLH and QMUL. Under the MTA and data sharing agreement (DSA) between the two institutions and with patient consent, the CRF will collect blood samples during pre-surgery operation and after the surgery during the first PSA follow-up visit at UCLH.

The following clinical data will be collected for each patient by the CRF:

- Histology reports
- Clinical stage
- Prostate Specific Antigen (PAS) (pre- and post-surgery)
- Imaging (MRI, PSMA-PET/CT and bone scan)
- Results and record of adjuvant therapies
- Treatment date and method for post-surgery cancer recurrence

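### Salvage hormones or radiotherapy are recorded at follow-up but have no place in the failure definitions, so a recurrence treated below PSA 0.2 can drop out of the event count

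*Protocol*

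**What the plan says.** **What is collected.** Protocol Section 6 lists three things to ascertain in men whose 3-month PSA is negative: a later PSA of 0.2 or more, metastasis on imaging, "or if they have received salvage treatment with hormones/radiotherapy". Section 9 adds to the data list "Treatment date and method for post-surgery cancer recurrence".

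**What counts as an event.** In Section 3, Table 1, treatment failure is a PSA at or above 0.2 at the 3-month test "and remaining at this level or further increase afterwards without further treatment, or imaging detected appearance of cancer lesions". BCR, in Table 1 and again under Definitions in Section 7, is a PSA of 0.2 or more "at any time post-RP and remaining at this level or further increase afterwards without further treatment". The method of analysis in Section 7 describes the primary event as RP treatment failure, "i.e. BCR or progression detected by any imaging at the 4.5-year follow-up time point". None of these names salvage treatment. For the full endpoint definitions Section 7 points to a Table 4, which is not in the protocol text at hand.

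**Who is analysed.** Section 5 sets a target of 200 men who, among other conditions, have no locally remaining disease "and do not subsequently have ADT (adjuvant ADT) or radiotherapy". The end of the method of analysis in Section 7 reports separately the men left out of the analyses, including those with a positive margin "and who subsequently have adjuvant ADT or radiotherapy".

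**The concern.** The protocol treats salvage therapy as worth asking about alongside PSA and imaging, yet gives it no status in any visible outcome definition. Table 1 says the combined endpoint is meant to capture clinically significant cancer as completely as possible, and a recurrence that was treated early is such an event. Men return to their referring centres after 3 months, so the timing of treatment is outside the study's control.

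Under the study hypothesis most men who recur are CTC-positive. If a treated recurrence is not an event, a correct positive is recorded as a false positive, and a CTC-negative man treated in the same way is recorded as a true negative. Section 7 itself says specificity matters because a positive test might later be used to withhold curative surgery.

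**Working it through.** **1. The plan's own figure.** Inputs from Section 7, Sample size: sensitivity 95%, precision 5 points either side, 95% CI, prevalence 40%, inflation 8.5%.

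- Events = 1.96² × 0.95 × 0.05 / 0.05² = 72.99, so 73.
- Men = 73 / 0.40 = 182.5, so 183.
- Inflated: 183 / (1 − 0.085) = 200.

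The stated 73, 183 and 200 reproduce. No figure in the plan is disputed.

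**2. How the text classifies the man in question.** He has a PSA rise below 0.2, receives salvage treatment, and afterwards shows no PSA of 0.2 or more and no lesion.

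- Table 1, treatment failure: neither component is met.
- BCR at any time: not met.
- Section 7, primary event: neither BCR nor imaging progression.
- Sections 5 and 7, exclusions: these name adjuvant ADT and radiotherapy, with no time limit. In Section 5 the word radiotherapy stands unqualified. He may or may not fall under them.

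He is either a non-failure or not in the analysis. On neither reading is he an event.

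**3. Size if he is kept.** Take 200 men, 80 true failures (0.40 × 200), sensitivity 95%, and true specificity 99% (a value mentioned in the sample size text) in the other 120. Let f be the share of true failures treated below 0.2 and never meeting the definition. The documents give no rate; f from 5% to 20% is assumed. CTC status is taken as unrelated to early treatment among failures.

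- Lost events m = 80f; events left = 80 − m.
- Half-width for sensitivity = 1.96 × √(0.95 × 0.05 / (80 − m)).
- Observed specificity = (0.99 × 120 + 0.05m) / (120 + m).
- Observed PPV = 0.95(80 − m) / (0.95 × 80 + 0.01 × 120).
- Men needed for 73 events = 73 / (0.40(1 − f)).

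| f | m | Events left | Half-width (points) | Specificity | PPV | Men for 73 events |
|---|---|---|---|---|---|---|
| 0 | 0 | 80 | 4.8 | 99.0% | 98.4% | 183 |
| 5% | 4 | 76 | 4.9 | 96.0% | 93.5% | 193 |
| 10% | 8 | 72 | 5.0 | 93.1% | 88.6% | 203 |
| 15% | 12 | 68 | 5.2 | 90.5% | 83.7% | 215 |
| 20% | 16 | 64 | 5.3 | 87.9% | 78.8% | 229 |

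Events fall below 73 once f exceeds 1 − 73/80 = 8.75%.

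**4. Sensitivity.** It stays at 95% if early treatment is unrelated to CTC status. If every lost failure is CTC-positive, it is (76 − m)/(80 − m): 72/76 = 94.7% at m = 4 and 60/64 = 93.8% at m = 16. At the opposite extreme, losing all four CTC-negative failures would make it read 100%.

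**5. Size if he is excluded.** The same 4 to 16 events are lost. Prevalence becomes 76/196 = 38.8% to 64/184 = 34.8%. Specificity is not diluted, but men leave the analysis because of something that happened after the blood sample was taken.

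**The case against.** **The classification is inferred.** A reader might infer that the protocol scores such a man as a surgical success. No sentence says so: his status follows from the definitions and could be changed by Table 4 or by an SAP not at hand. This stands as a limit on the wording. BCR is nevertheless written out in full in Section 7, without salvage, and what counts as an event is fixed in the protocol.

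**He might be excluded.** The untimed exclusions in Sections 5 and 7 can be read to remove him, and then specificity is untouched. This also stands as a possible reading. Against it, both places say adjuvant while Section 6 uses salvage as a separate term. Section 2.1 says men who recur usually go on to radiotherapy and hormones, so a rule removing everyone later treated would take out many of the events the sample size relies on.

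**He may still become an event.** A reader might also infer that a man treated early can never be a failure. That goes too far. The condition about no further treatment may govern only confirmation after 0.2 has been reached, so a later sustained PSA of 0.2 or more could still count. A lesion on imaging counts in any case.

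**Specificity is secondary and already caveated.** The primary analysis is sensitivity, which is little affected in the plausible direction. Section 7 expects low specificity and plans further analyses assuming up to 20% of events come after the funded period. Those analyses address late events; a recurrence controlled by salvage may never meet the definition however long follow-up runs.

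**Conclusion.** The point holds as a gap in the endpoint definition. Salvage treatment is ascertained and dated but is not a component of post-RP treatment failure or BCR in the visible text, and the exclusion wording leaves unclear whether the men concerned are kept. A recurrence treated below 0.2, with no later PSA or imaging event, is lost on either reading.

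The harm falls mainly on specificity and PPV and on the number of events; the effect on the primary sensitivity estimate is small. All sizes rest on an assumed share of 5% to 20% of 80 failures, and the specificity and PPV losses arise only if the men are kept.

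A larger loss might be inferred by holding 120 apparent non-failures fixed and supposing 20 of them were treated early: (0.99 × 100 + 0.05 × 20)/120 = 83.3%. That implies 80 + 20 = 100 true failures in 200, or 50%, against the planning value of 40%, so it should not be taken as the plan's exposure.

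**What to change.** For outcome scoring only, with no implication for when anyone is treated:

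- Add the start of salvage hormones or radiotherapy for PSA rise or recurrence as an event in post-RP treatment failure and BCR-free survival, dated at treatment start unless a PSA or imaging event came earlier.
- Keep treatment given for surgical pathology alone, without PSA rise, as a separate category.
- State in Sections 5 and 7 that the exclusions cover adjuvant and not salvage treatment, and bring Table 1, Section 7 and Table 4 into line.
- Report the PSA/imaging-only endpoint as a sensitivity analysis.

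The cost is about a sentence in each place; the treatment data and dates are already to be collected. The drawback is that the event then partly reflects practice at the referring centres. It cannot reflect the CTC result as long as the blinding of patients and treating clinicians in Table 1 holds, and the sensitivity analysis shows how far practice matters.

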Study objectives and endpoints	
Objectives are set in the context of high-risk patients diagnosed with localised prostate cancer scheduled for robot-assisted RP who have not had neoadjuvant ADT, and are listed below.
 
Primary objectives:
 
To establish the value of CTC positivity in predicting post-RP treatment failure, including BCR and new lesions detected by cancer imaging.
 
To establish the value of a combined CTC test (including CTC enumeration and gene expression) in predicting post-RP treatment failure and the time of the development of BCR and new lesions detected by cancer imaging.
 
Secondary objectives
 
To investigate the potential of CTCs in predicting positive lymph node metastasis, which affects the selection and scale of RP as the initial treatment.
 
To assess potential for convenient non-invasive disease monitoring

Protocol for spin off research project- Circulating tumour cells as biomarkers to predict prostate cancer metastasis for treatment stratification of localised cancer

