- Contacting patients on an annual basis for 10 years so they may report their PSA and relevant further treatments. Methods of contact will be decided upon with PPI and may consist of list of preferred options including phone call by the CRF and/or use of secure electronic means via automated email prompts, secure website or app data entry. [name] is currently collaborating with primary care colleagues to develop a patient support app under a separate funding support.
- Flagging and linkage to the patients' relevant electronic health data using their NHS number and date of birth. Under the Confidentiality Advisory Group (CAG), we will request treatment, imaging and cancer outcome data from NHS Digital based on ONS-HES-DID (Data Imaging Data) and NCRAS data sets.

We would thus be able to plan analyses of the diagnostic accuracy and predictive value of the CTC-based tests in terms of metastases and progression-based outcomes at 7.5 years and 10 years of follow-up. Further longer-term follow-up after the 10-year will be performed by accessing the GP and NHS digital records if required and with further ethical approval.

Patient recruitment, sample collection and follow-up procedure were summarised in Table 2
Table 2. Patient recruitment, sample collection and follow-up procedure

Procedure	Screening/Baseline	Pre-RP	3 months post op	12 month post op	24 month post op	... each year...	120 month post op
-----------	--------------------	--------	------------------	------------------	------------------	------------------	-------------------

Protocol for spin off research project- Circulating tumour cells as biomarkers to predict prostate cancer metastasis for treatment stratification of localised cancer

Eligibility assessment	x						
Informed Consent	x						
Blood Sample collection		x	x				
PSA		x	x	x	x	x	x
Medical record review and online app/phone follow-up (PSA and/or Adjuvant therapies) rates of BCR, metastasis, other progression events and death				x	x	x	x

7. Evaluating the efficiency of CTC positive score and the gene panel in predicting RP treatment failure.

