Accuracy of the CTC scores alone and in combination with CTC gene panel expression data in determining RP treatment failure, i.e. BCR and/or metastasis via imaging, in particular PSMA-PET, over the study period will be measured. The prognostic value of CTC data will also be investigated for BCR, PSMA-PET detected cancer lesions, metastasis event, overall survival and cancer specific survival outcomes (see below statistical analysis plan section). At the end of this project, we expect to generate robust data to determine whether CTCs detectable in patients with high-risk localised PCa at pre- and post-RP can predict RP treatment failure and a CTC gene panel will further enhance the prediction value of CTCs for post-RP cancer progression.

Statistical methodology and analysis

The primary analysis is the estimation of the sensitivity of the pre-surgery CTCs for detection of RP treatment failure, i.e. BCR or progression detected by imaging. Observed specificity, positive and negative prediction values will be reported. Prevalence of events and specificity will be presented over time. BCR-free survival will be estimated and Kaplan-Meier curves presented. Preliminary investigation of the prognostic value of pre-surgery CTC data in terms of predicting survival outcomes will be investigated. CTC data will be explored alongside other pre-surgery risk factors using multivariate analysis. Recurrence events and follow up CTC results will be reported and compared over time.

Statistical considerations

1). Definitions:

- **CTC score and result:** CTCs will be identified based on the immunofluorescence staining as CK⁺/VIM⁻/CD45⁻, CK⁺/VIM⁺/CD45⁻, and CK⁻/VIM⁺/CD45⁻ CTCs as described above in lab procedure Part IV. Positive CTC score were defined based on our previous data as any CK⁺/VIM⁺/CD45⁻, CK⁺/VIM⁺/CD45⁻ and/or >3 CK⁻/VIM⁺/CD45⁻ cells identified in the PCa patients.
- **CTC gene-expression result:** a binary (negative/positive) result based on the gene-expression profile from within the blood sample indicating the amount of genes expressed in CTCs from the PCa patients.

Protocol for spin off research project- Circulating tumour cells as biomarkers to predict prostate cancer metastasis for treatment stratification of localised cancer

- **Combined CTC result:** a binary (negative/positive) result based on both CTC number and gene-expression profile where a positive result indicates a patient should be considered to have high metastatic potential.

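### The only post-operative CTC sample is drawn at the 3-month visit whose PSA result can itself be the failure event, so for those men it is concurrent with the outcome and cannot predict it

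*Protocol*

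**What the plan says.** **Sampling.** Section 6 takes CTC blood "during the pre- and post-RP PSA test blood sampling". Section 9 places the post-operative draw "after the surgery during the first PSA follow-up visit at UCLH", and section 6 puts that visit 3 months after surgery. In the follow-up table of section 6, the row "Blood Sample collection" is marked only before surgery and at 3 months. Nothing is marked from 12 to 120 months. Collection runs over months 1 to 27.

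**Outcome at the same visit.** Section 6 says that a PSA of 0.2 or more at 3 months "will be recorded as a treatment failure event and PSMA-PET scans will be performed as standard clinical care". Men with a negative PSA at that visit are then followed for later recurrence, metastasis and salvage treatment. Table 1 ties the PSA part of the primary endpoint to the 3-month test.

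**Use of the sample.** Section 7 expects the study to determine whether "CTCs detectable in patients with high-risk localised PCa at pre- and post-RP can predict RP treatment failure". Its method of analysis adds: "Recurrence events and follow up CTC results will be reported and compared over time". It also correlates the gene panel with the change in CTC number across surgery and with progression events. Table 1 lists a secondary objective: "To assess potential for convenient non-invasive disease monitoring".

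**Primary analysis.** This is the sensitivity of the pre-surgery sample only.

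**The concern.** To predict an event, a marker must be measured before it. Here the post-operative marker and the PSA value that qualifies a man as a failure come from the same visit, so the lead time for those failures is zero. The later requirement that PSA stay at that level or rise does not create lead time, because the qualifying value is already on record.

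If these men are counted as predicted failures, a test that merely marks disease already visible on PSA could appear prognostic. The same applies to the pre-to-post change, since its second value is the 3-month sample.

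A related difficulty is that a comparison over time and a monitoring objective suggest a post-operative series, whereas the schedule supplies one point.

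**Working it through.** **1. Samples per man.** There are two in all, one of them after surgery. The collection window agrees: 24 months of recruitment plus 3 months is month 27. Two points give one change and no post-operative series.

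**2. Timing against outcome.**

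| Event | Time relative to post-operative CTC sample |
|---|---|
| PSA ≥ 0.2 at the 3-month test | Same visit |
| Later PSA recurrence in men negative at 3 months | After |
| Later imaging lesion, metastasis, death | After |

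Only the first row is concurrent. The protocol text does not separate it from the others when it speaks of post-operative prediction.

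**3. The plan's own sample size.** Inputs from section 7: sensitivity 95%, precision ±5 points, 95% interval, prevalence 40%, inflation 8.5%.
- Events: 1.96² × 0.95 × 0.05 / 0.05² = 72.99, so 73.
- Men: 73 / 0.40 = 182.5, so 183.
- Inflated: 183 / (1 − 0.085) = 200.

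The figures reproduce. They size the pre-surgery test and do not depend on this point.

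**4. Events left after a 3-month landmark.** Expected failures among 200 men: 0.40 × 200 = 80. The share *f* already present at 3 months is not in the protocol, so a range is assumed. Remaining events are *e* = 80 × (1 − *f*). As a yardstick only, the half-width at 95% sensitivity is 1.96 × √(0.95 × 0.05 / *e*). The protocol sets no such target for the post-operative sample.

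| Assumed share at 3 months | Events left of 80 | Half-width (points) | Events left of 73 | Half-width (points) |
|---|---|---|---|---|
| 10% | 72 | 5.0 | 66 | 5.3 |
| 25% | 60 | 5.5 | 55 | 5.8 |
| 50% | 40 | 6.8 | 36 | 7.1 |
| 75% | 20 | 9.6 | 18 | 10.1 |
| 100% | 0 | not estimable | 0 | not estimable |

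**5. Which row applies depends on the endpoint wording.** Read literally, Table 1 places every PSA-based primary failure at the 3-month test, which leaves only later imaging lesions to predict. Sections 6 and 7 count recurrence or imaging progression during follow-up, up to 4.5 years in section 7, which leaves later PSA failures as well. The two readings give very different numbers of usable events.

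**6. Illustration of what pooling could do.** All inputs here are assumed. The share at 3 months is 20–50%. The post-operative test is positive in 90% of those men and in a fraction *q* = 20–30% of everyone else, and it carries no information on later failure.
- Pooled sensitivity = *f* × 0.9 + (1 − *f*) × *q*. The lowest value is 0.2 × 0.9 + 0.8 × 0.2 = 0.34. The highest is 0.5 × 0.9 + 0.5 × 0.3 = 0.60.
- With 73 failures and 110 non-failures (183 − 73), take *f* = 0.5 and *q* = 0.2. The positives are 40.15 failures and 22 non-failures, a risk of 0.646. The negatives are 32.85 and 88, a risk of 0.272. The relative risk is 2.38.
- The other three corners give 1.36 (*f* = 0.2, *q* = 0.3), 1.50 (0.2, 0.2) and 2.07 (0.5, 0.3).

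The relative risk of 1.0 for later failure is an input to this example, not a result.

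**The case against.** The strongest reply is that the protocol specifies no accuracy analysis of the post-operative sample. The primary sensitivity, the Cox regression and the multivariate work all name pre-surgery data. The analyses that explicitly use post-operative results are descriptive or correlational. The prediction sentence is an expectation about a question, not a method. Time zero and risk sets for a secondary analysis commonly belong in a statistical analysis plan, which is not at hand.

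Much of this stands. The primary analysis is untouched, and the relative risks above model an analysis that the protocol does not spell out. Three things remain:
- The prediction statement covers the post-operative sample by name, and the general accuracy statement in section 7 is not restricted to the pre-surgery sample.
- The sampling schedule, the endpoint and the monitoring objective are all fixed in the protocol. An analysis plan cannot add post-operative samples.
- The endpoint wording in Table 1 and in sections 6 and 7 needs reconciling in the protocol itself.

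It is also fair to say that the monitoring objective is modest, asking only about potential. One pre-to-post change related to later events is a legitimate first look if it is described as such.

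A reader might infer that the 3-month sample can predict nothing. The documents do not support that. Section 6 already identifies and follows the men who are PSA-negative at 3 months, and for them later events are a proper prospective target.

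**Conclusion.** The point holds for the post-operative sample. It coincides with any failure defined by the 3-month PSA, so it cannot support a claim to predict those failures, and it gives no post-operative series for monitoring. This rests on the protocol's own schedule and definitions, not on any assumed figure.

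The number of events left for a valid post-operative analysis cannot be fixed from the document. It falls from 80 to between 72 and 20 for assumed 3-month shares of 10–75%, and no PSA-based primary failures remain if Table 1 is read literally.

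Two stronger inferences are not supported. The first is that the study's main result is compromised: the 73, 183 and 200 figures and the pre-surgery sensitivity analysis do not use this sample. The second is that the relative risks of 1.4–2.4 estimate a bias: they show only that pooling could make an uninformative test look prognostic under assumed inputs.

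This is a secondary-analysis matter that should be corrected.

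**What to change.** 1. For any analysis that relates the post-operative CTC result, or the pre-to-post change, to outcome, use a 3-month landmark. Include men without failure at that visit and count time from the sample.
2. Report men already failing at 3 months separately, as a cross-sectional association.
3. Amend the prediction statement in section 7 to match. Limit the monitoring objective and the comparison over time to the change from before surgery to 3 months and its relation to later events.
4. Reconcile the Table 1 primary endpoint with sections 6 and 7, since this sets how many events remain after the landmark.

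No new data are needed, because follow-up already separates men by their 3-month PSA. The cost goes beyond wording: the landmark changes the analysis set, lowers the event count as tabulated above and narrows the monitoring claim. The primary analysis and recruitment target stay as they are.
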